1. OBJECTIVES

This study is a phase II study of the JAK kinase inhibitor INCB018424 phosphate in patients with advanced hematological malignancies who have failed prior therapy. The objectives of the proposed study are:

Primary:

To observe the anti-tumor effects of INCB018424 in patients with relapsed/refractory AML, ALL, and MDS (including CMML), and blast phase or tyrosine kinase refractory CML.

Secondary:

- 1. To determine the safety and tolerability in patients with relapsed/refractory AML, ALL, and MDS (including CMML), and blast phase or tyrosine kinase refractory CML.
- 2. To determine the pharmacokinetics and preliminary pharmacodynamic activity including the modulation of signal transducer and activator of transcription (STAT) protein phosphorylation.

2. BACKGROUND

2.1 Diseases to be studied

Despite progress in leukemia therapy, most adult patients with leukemia still die from disease progression, and improvements in therapy are still required for pediatric patients with resistant or relapsed leukemia. For patients with acute myeloid leukemia (AML) who fail to achieve a complete remission (CR) with first attempts at induction or who have relapsed disease, current therapy is inadequate with a true long term cure rate of less than 10% and therefore, new agents are needed. Adult patients with acute lymphocytic leukemia (ALL) who fail to achieve a CR with first attempts at induction or who have relapsed disease have a true long term cure rate of less than 10%. Patients with chronic myelogenous leukemia (CML) who enter blastic phase having received prior imatinib therapy or who fail imatinib therapy for blastic phase have a median survival of 3 to 9 months with current therapies. Similarly, patients with CML who have failed two or three tyrosine kinase inhibitors have few alternative options.

2.2 INCB018424 Phosphate

2.2.1 Drug Product

INCB018424 phosphate is an inhibitor of the Janus kinase family of protein tyrosine kinases (JAKs) that is currently being developed for treatment of myeloproliferative disorders under IND No. 77,456. Unless otherwise

noted, INCB018424 phosphate is referred to throughout this IND as INCB018424. INCB018424 Phosphate Tablets 5 and 25 mg (free base equivalent), as disclosed in IND No. 77,456, will be used in the proposed studies described in this IND. Additional details of the CMC characterization of INCB018424 may be found in the Clinical Investigators Brochure (CIB).

IND No. 77,455 was submitted to the FDA Division of Anesthesia, Analgesic, and Rheumatology Products to develop INCB018424 Phosphate Capsules for the treatment of patients with rheumatoid arthritis. Phase 1 of this study (Study INCB 18424-132) has safely completed the short term (10 day) dosing of normal volunteers with the 25 mg BID doses of INCB018424 that are proposed to be used in this study.

2.2.2 *In Vitro* Pharmacology of INCB018424

INCB018424 is a potent inhibitor of all JAK family members (IC $_{50}$ values < 5 nM), with modest selectivity for JAK2. It does not significantly inhibit a broad panel of 26 other kinases when tested at concentrations approximately 100 fold higher than its potency against the various JAKs. Moreover, in cell-based assays relevant to the pathogenesis of MPDs and cancer, such as cytokine-induced JAK-STAT signaling, cytokine-driven tumor cell proliferation as well as growth of a cell line expressing the JAK2V617F mutation, INCB018424 demonstrates excellent potency (IC $_{50}$ values of ~ 80-150 nM). This effect is not due to general cytotoxicity, because INCB018424 (up to 20 μ M) had no significant effect on the growth of cytokine-independent cell lines. In addition, INCB018424 inhibits cytokine-induced JAK/STAT phosphorylation in human whole blood with an IC $_{50}$ value of ~ 300 nM, providing a useful biomarker of INCB018424 pharmacological activity. Additional details as to the *in vitro* pharmacology of INCB018424 may be found in the Clinical Investigators Brochure (CIB).

2.2.3 In Vivo Pharmacology of INCB018424

Treatment of mice with orally administered INCB018424 resulted in a dose-dependent suppression of STAT3 phosphorylation and tumor growth in the cytokine-dependent multiple myeloma INA-6 xenograft model at doses ≥ 10 mg/kg BID. Moreover, oral administration of INCB018424 inhibited JAK pathway signaling, tumor cell growth and splenomegaly in mice resulting from intravenous inoculation of a BaF3 cell line engineered to express JAK2V617F (BaF3-JAK2V617F). Additional details as to the *in vivo* pharmacology of INCB018424 may be found in the Clinical Investigator's Brochure (CIB).

Pharmacological data obtained in both *in vitro* and *in vivo* model systems support the potential utility of orally administered INCB018424 in the treatment of JAK-dependent hematological malignancies.

INCB018424 has been administered orally in single doses to healthy subjects in ongoing study INCB 18424-131. In study INCB 18424-131, single oral doses of 5 mg, 10 mg, 25 mg, 50 mg, 100 mg and 200 mg have been administered with monitoring of adverse events, clinical laboratories, PK and pharmacodynamic parameters. All single doses were well tolerated with no observed drug-associated adverse events. The pharmacodynamic preliminary, unaudited draft data available indicate that single doses of INCB018424 are able to inhibit interleukin-6 induced STAT3 phosphorylation in a dose dependent manner. The 200 mg dose of 18424 produced ~80-95% inhibition of STAT3 phosphorylation between 1-8 hours following dosing with levels returning to baseline by 48 hours.

In study INCB 18424-132, multiple oral doses of 25 mg BID and 50 mg daily and BID have been administered with monitoring of adverse events, clinical laboratories, PK and pharmacodynamic parameters. The preliminary unaudited pharmacodynamic draft data available indicate that multiple doses of INCB018424 are able to inhibit interleukin-6 induced STAT3 phosphorylation in a dose dependent manner, similar to data obtained in the single dose studies. The data on day 1 and day 10 demonstrated similar levels of inhibition of STAT3 phosphorylation, indicating a lack of cumulative biological activity. From an evaluation of the safety data obtained in this study, the preliminary conclusion is that the INCB018424 50 mg BID dose is considered too high for healthy volunteers and patients without serious diseases. Dosing in these populations should be limited to 25 mg BID or lower and up to 50 mg daily, although higher doses than 50 daily may be safe but have not been tested beyond single doses. However, in patients with malignancies dose escalation could continue until the maximum tolerated dose is achieved due to the different benefit-risk ratio in these subjects and because these patients may respond differently.

Under IND No. 77,456, INCB018424 has also been dosed to three patients with multiple metaplasia with myelofibrosis at 25 mg BID for over five months with clinical benefit but without notable toxicity. In this study four patients have also been dosed at 50 mg INCB018424 BID but, according to protocol, dosing was halted after two of four subjects presented with significant reductions in peripheral blood neutrophils and platelets. Subsequently, according to protocol, three additional patients have been treated at the 25 mg BID dose for at least 1 month to establish this dose as the MTD in this population.

2.3 Rationale

The Jak family of kinases comprises four proteins (Jak1, Jak2, Jak3, and Tyk2) that can associate with cytokine receptor subunits, phosphorylate them, and in doing so create docking sites on the receptors for binding of

SH2-containing proteins. In general, Jaks consist of several domains (JH1-JH7), including a tyrosine kinase domain, and the functional significance of these domains has been characterized by mutational analysis. Jaks are able to associate with the cytokine receptors as well as with each other. Dimerization/oligomerization of cytokine receptor subunits as a result of ligand binding leads to juxtaposition of Jaks. This results in transphosphorylation and activation of their kinase activity and the phosphorylation of downstream signaling proteins such as Stats, *Src*-kinases, and adaptors such as Shc, Grb2, and Cbl.⁴

Abnormalities of Jak function have been associated with a number of disorders. For example, chromosomal translocations resulting in TEL-JAK2 constructs lead to the constitutive activation of STAT5, IL-3-independent cellular proliferation, and leukemogenesis. The translocation t(9;12)(p24;p13) results in the fusion of the kinase catalytic region of JAK2 with the transcription factor TEL generating the constitutively active TEL-JAK2. Similarly, infection with oncogenic viruses such as human T-cell lymphotrophic virus, type I, and Abelson murine leukemia viruses results in enhanced kinase activity of Jaks, possibly accounting for their leukemogenic potential.

The STAT transcription factors are coded by six known mammalian genes and include 10 different STAT proteins including different isomers of STATs 1, 3, 4, and 5. Like other transcription factors STATs have a well-defined structure including a DNA-binding domain, a conserved NH₂-terminal domain, a COOH-terminal transactivation domain, and SH2 and SH3 domains. Their activation through tyrosine phosphorylation results in their dimerization and translocation into the nucleus where they activate specific genes.⁴

Jak proteins activate a number of intracellular signaling proteins, among which STATs are the best defined. Binding of a cytokine to its receptor rapidly induces tyrosine phosphorylation of the cytoplasmic domains of the receptor by activated Jak kinases, thus providing a docking site for STAT proteins, which are then phosphorylated. This phosphorylation of STATs leads to their homo- or heterodimerization and translocation to the nucleus, followed by DNA binding and gene activation. The specificity for STAT phosphorylation is determined by the receptor docking sites and not the Jak kinases. Also, different STAT proteins have different DNA-binding affinities, resulting in activation of specific genes. STATs also interact with other transcription factors such as the p300/cyclic AMP-responsive element binding protein family of coactivators to activate genes. The transcriptional activity of STATs may also be regulated by the phosphorylation of their serine and threonine residues, although the implications of such regulation are not known.

STATs mediate diverse and sometimes opposite cellular events affecting growth, differentiation, and apoptosis. For example, STATs can mediate both growth arrest and cellular proliferation. Specifically, STAT1 mediates the growth-inhibitory effects of IFN-7, through the induction of the CDKI p21^{waf1}, whereas STAT5 mediates proliferative effects of IL-3 and GM-CSF. Similarly, phosphorylation of STAT3 can result both in IL-6- and IL-10-induced growth arrest, and in GM-CSF- and IL-3-induced proliferation. STATs also modulate cellular differentiation and apoptosis. Reconstitution of STAT1 in STAT1-null U3A cells (which do not respond to TNF-a) restores basal caspase expression and renders them sensitive to TNF-induced apoptosis. Conversely, STAT3 and STAT5 mediate the antiapoptotic effects of IL-6 and IL-2, respectively. STAT1 activates the caspase cascade through up-regulation of Fas and FasL expression in response to IFN-7. The exact mechanisms underlying these diverse effects are being elucidated.⁴

Abnormalities of the JAK-STAT pathways have been described in a variety of leukemias and their inhibition can be a goal for leukemia therapy.

3. PATIENT ELIGIBILITY

Patients in this trial can be of any race and either gender.

3.1 Inclusion Criteria

- A. Must be at least 18 years of age.
- B. Patients must have relapsed/refractory leukemias for which no standard therapies exist. Patients with poor-risk myelodysplasia (MDS) [i.e. refractory anemia with excess blasts (RAEB-1 or RAEB-2) by WHO classification] and chronic myelomonocytic leukemia (CMML) who failed prior therapy are also candidates for this protocol. Relapsed/refractory leukemias include acute non-lymphocytic leukemia (AML) by WHO classification (i.e. ≥ 20% blasts), acute lymphocytic leukemia (ALL), or chronic myelogenous leukemia (CML) in blast crisis. Patients with CML who are resistant to at least two tyrosine kinase inhibitors and have no standard stem cell transplant option are also eligible.
- C. ECOG performance status of 0-2.
- D. A female of childbearing potential must have a negative serum or urine pregnancy test at screening. Women of child-bearing potential (i.e., women who are premenopausal or not surgically sterile) must use acceptable contraceptive methods (abstinence, intrauterine device [IUD], oral contraceptive or double barrier device), and must have a negative serum or urine pregnancy test within 2 weeks prior to beginning treatment on this trial. Sexually active men must also use acceptable contraceptive methods for the duration of time on study.

- E. Must be able and willing to give written informed consent.
- F. In the absence of rapidly progressing disease, the interval from prior treatment to time of study drug administration should be at least 2 weeks for cytotoxic agents, or at least one week for noncytotoxic agents. Persistent clinically significant toxicities from prior chemotherapy must not be greater than grade 2.
- G. Patients must have the following clinical laboratory values unless considered due to leukemic organ involvement:
 - 1. Serum creatinine ≤ 2.0 mg/dl.
 - 2. Total bilirubin ≤ 1.5x the upper limit of normal unless considered due to Gilbert's syndrome or hemolysis.
 - 3. Alanine aminotransferase (ALT), and aspartate aminotransferase (AST) \leq 2.5x the upper limit of normal unless considered due to organ leukemic involvement (then \leq 5x the upper limit of normal).
 - H. Patients with active CNS disease are included and will be treated concurrently with intrathecal therapy. INCB018424 will not be administered by intrathecal route.

3.2 Exclusion Criteria

Patients with any one of the following criteria will not be eligible for study participation:

- A. Uncontrolled intercurrent illness including, but not limited to uncontrolled infection, symptomatic congestive heart failure, cardiac arrhythmia, or psychiatric illness/social situations that would limit compliance with study requirements.
- B. Active heart disease including myocardial infarction within the previous 3 months, symptomatic coronary artery disease, arrhythmias not controlled by medication, or uncontrolled congestive heart failure.
- C. Current treatment or treatment within 2 weeks or 5 half-lives (whichever is longer) prior to the first dose of study medication with another investigational medication or current enrollment in another investigational drug protocol (unless there is evidence of rapidly progressive disease in which case a shorter interval from last therapy may be acceptable).
- D. Females who are pregnant or are currently breastfeeding.
- E. Patients receiving therapy with intermediate or high dose steroids greater than the equivalent of 10 mg prednisone per day are not allowed.

- F. Evidence of active hepatitis or human immunodeficiency virus (HIV) infection determined by screening laboratory test results or results within prior 3 months.
- G. Any unresolved toxicity equal to or greater than Grade 2 from previous anticancer therapy, except for stable chronic toxicities not expected to resolve, such as peripheral neurotoxicity.
- H. Incomplete recovery from any prior surgical procedures or had surgery within 4 weeks prior to study entry, excluding the placement of vascular access.
- Uncontrolled intercurrent illness or any concurrent condition that, in the Investigator's opinion, would jeopardize the safety of the patient or compliance with the protocol.
- J. In patients who are receiving medications known to be inhibitors or inducers of CYP3A4 every effort will be made to change these medications to acceptable alternatives. If this is not safely possible, patients will be excluded from participation in the study. If a patient is already on the study, must be started on a CYP3A4 inhibitor, and is demonstrating benefit from the study, they will be seen twice weekly in the first cycle and weekly in the subsequent cycles for toxicity evaluation and their dose will be modified according to the table in section 4.5 in the event of a toxicity thought to be related to the study drug. A list of CYP3A4 inducers and inhibitors is provided in Appendix I.

4. TREATMENT PLAN

4.1 Dose of INCB018424 and Treatment Cycle

This is a phase II study of oral INCB018424 in patients with relapsed/refractory AML, ALL, and MDS (including CMML), and blast phase or tyrosine kinase refractory CML. The starting dose of INCB018424 will be 25 mg po twice daily, which has been determined to be the maximum tolerated dose in patients with myelofibrosis with myeloid metaplasia and a dose that is tolerated for ten days in normal human volunteers.

INCB018424 will be administered orally at a dose of 25 mg BID for 7 days each week for 4 weeks (cycle number 1). Patients will be evaluated after 1 full cycle of therapy (28 days) for response. Responding patients or patients with stable disease will be allowed to continue on study at a dose of 25 mg INCB018424 BID until progression. The response assessment for the purpose of study statistical evaluation will be after two cycles (8 weeks) of therapy. Patients with progressive disease, based on clinical and laboratory evaluation, will, at the discretion of the Investigator, either be removed from the study or, as long as the 25 mg BID dose has been well tolerated, dose escalated to 50 mg INCB018424 BID. In instances of dose escalation to 50mg BID, patients will be evaluated after

1 full cycle of therapy (28 days) for response and toxicity. At that point, patients with continued progressive disease, based on clinical and laboratory evaluation, will be removed from the study. In instances of dose escalation, the response assessment for the purpose of study statistical evaluation will be after two cycles (8 weeks) of therapy at the 50 mg BID dose.

Patients with chronic phase CML who have failed at least 2 prior tyrosine kinase inhibitors and do not have a standard transplant option will be assessed for response after 3 months of therapy in the absence of loss of disease control and they may continue therapy if they demonstrate any clinical benefit. Patients with chronic phase CML will not be allowed to have the dose escalation as this population has less of a life-threatening disease situation.

Patients who, in the opinion of the Investigator, are demonstrating cytopenias not thought to be related to disease progression and who may be receiving benefit from treatment may, at the discretion of the Investigator, be dose adjusted to a lower dose of INCB018424 BID or an equivalent dose given daily (see section on dose modifications below). Studies in subjects with myelofibrosis with myeloid metaplasia using different doses and schedules of INCB18424 may be used as a guide to dose adjustments in this study.

Patients will initiate the first cycle of therapy at MDACC. They will have weekly visits at their local physician's office with physical exam and review of symptoms during cycle one. In the absence of intolerable side effects, patients may return to the local oncologist for laboratory tests, but only MDACC investigators can make treatment decisions. Patients will return to MDACC every 4 weeks to be evaluated and receive their new supply of study medication. For the second and third cycle, patients will return to MDACC every 4 weeks to be evaluated and receive their new supply of study medication. Subsequently, patients will return to MDACC every three months. Because of drug stability issues, some patients may have to continue to be seen on a monthly basis to have the drug provided.

For toxicity evaluation, patients enrolled in the study will be considered in 2 cohorts (I) those with relapsed/refractory AML, ALL, and MDS (including CMML), and blast phase CML, and (II) those with chronic phase CML. At any time after 6 patients are enrolled in cohort I (including AML, ALL, MDS, blast phase CML patients), if 30% or more patients experience grade 3 or 4 toxicity thought to be directly related to INCB018424 and lasting longer than 2 weeks, then we will stop that cohort of the trial. At any time after 6 patients are enrolled in cohort II (including chronic phase CML patients), if 15% or more patients experience grade 3 or 4 toxicity thought to be directly related to INCB018424 and lasting longer than 2 weeks, then we will stop that cohort of the trial.

4.2 Administration of INCB018424

This is an open label, non-randomized, study of INCB018424, administered orally to patients with relapsed/refractory AML, ALL, and MDS (including CMML), and blast phase or tyrosine kinase refractory CML. The study of INCB018424 in each disease listed will be conducted in two parts. The first part is intended to enroll a maximum of 10 patients within each of the four disease categories included in this study and to identify whether significant benefit is observed. If a minimum of one patient shows benefit that is considered significant, there will be an expanded cohort of 20 additional patients treated in that arm of the study.

Patients will receive 50 mg/day administered orally in two divided doses (i.e., BID: every 12 hours \pm 2 hours). Within each arm of the study, three patients will be initially treated and observed for toxicity for one treatment cycle (28 days) before the additional seven patients are entered. Dose reduction will be considered if the number of patients experiencing grade 3 or higher toxicities exceed 2/3, 3/4, 4/7, 5/10, 6/14, 7/18, 8/22, 9/26. Treatment will be administered primarily on an outpatient basis, but can be administered as an inpatient if the patient is hospitalized for other reasons.

The 5 mg tablets have been shown to be stable when stored up to one month at 25° C/60%RH and 40° C/75%RH; the 25 mg tablets have been shown to be stable when stored for three months at 25° /60%RH and 40° /75%RH. (25° C = 77° F, 40° C = 104° F).

4.3 Supportive Care Guidelines

Supportive measures including erythropoietin, analgesics, blood transfusions, antimicrobials, and hematopoietic colony stimulating factors for treatment of cytopenias are permitted.

Prophylactic use of hematopoietic colony stimulating factors is not permitted.

Other chemotherapy, investigational cytotoxic agents, radiation, or biologic therapy is prohibited while the patient is on study with the following exceptions during cycle 1: During the first 7 days of study only, patients may receive leukaphereses (not more than three procedures per week and not more than five procedures in total to control elevated blast and/or platelet counts and/or hydroxyurea (up to a maximum of 5 gm/day) for a maximum of 14 days. Intrathecal chemotherapy to treat isolated CNS involvement of leukemia is allowable.

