6. RESPONSE DEFINITIONS

Patients will be assessed for efficacy at the end of each 28 day cycle of therapy, +/-4 days for the first 3 cycles, then 3 monthly thereafter.

6.1 Acute leukemias, MDS, CML-BP, CMML:

- 6.1.1 Complete remission: The patient must be free of all symptoms related to leukemia and have an absolute neutrophil count $\geq 1 \times 10^9 / L$ and platelet count $\geq 100 \times 10^9 / L$, and normal marrow differential ($\leq 5\%$ blasts) in a normo- or hypercellular marrow.
- 6.1.2 Partial remission: CR with 6-25% abnormal cells in the marrow or 50% decrease in bone marrow blasts.
- 6.1.3 CRp: As per CR but platelet count <100 x109/L.
- 6.1.4 Hematologic Improvement (HI)

Hematologic improvement should be described by the number of individual, positively affected cell lines (e.g. HI-E; HI-E + HI-N; HI-E+ HI-P + HI-N).

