6.1.4.1 Erythroid response (HI-E)

Major response: For patients with pretreatment hemoglobin less than 11 g/dL, greater than 2 g/dL increase in hemoglobin; for RBC transfusion-dependent patients, transfusion independence.

Minor response: For patients with pretreatment hemoglobin less than 11g/dL, 1 to 2 g/dL increase in hemoglobin; for RBC transfusion-dependent patients, 50% decrease in transfusion requirements.

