6.1.4.3 Neutrophil response (HI-N)

Major response: For absolute neutrophil count (ANC) less than 1.5×10^9 /L before therapy, at least a 100% increase, or an

absolute increase of more than $0.5 \times 10^9/L$, whichever is greater.

Minor response: For ANC less than 1.5×10^9 /L before therapy, ANC increase of at least 100%, but absolute increase less than 0.5×10^9 /L.

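### Hematologic improvement is scored on raw blood counts while growth factors and transfusions are permitted, so supportive care can be counted as drug response

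*Combined protocol and SAP*

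**What the plan says.** **Supportive care (4.3).** Erythropoietin is allowed, and in the same sentence "blood transfusions, antimicrobials, and hematopoietic colony stimulating factors for treatment of cytopenias are permitted". The only limit on growth factors is that "Prophylactic use of hematopoietic colony stimulating factors is not permitted". No interval is set between support and a response assessment.

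**Hematologic improvement (6.1.4).** Major HI-E reads "For patients with pretreatment hemoglobin less than 11 g/dL, greater than 2 g/dL increase in hemoglobin". A separate branch for red-cell transfusion-dependent patients is scored on transfusion independence (major) or a halved requirement (minor). Major HI-P is a platelet rise of at least 30 x10^9/L from a baseline below 100, again with a branch for transfusion-dependent patients. The HI-N rule opens "Major response: For absolute neutrophil count (ANC) less than" 1.5 x10^9/L. It asks for a 100% increase or a rise above 0.5 x10^9/L, whichever is greater; a doubling with a smaller absolute rise is minor.

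**Complete remission (6.1.1).** "The patient must be free of all symptoms related to leukemia and have an absolute neutrophil count" of at least 1 x10^9/L, with platelets of at least 100 x10^9/L and a "normal marrow differential" in a normo- or hypercellular marrow. CRp is the same with platelets below 100.

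**Expansion.** Section 9.1.1 expands a category after at least one response in 10. Section 4.2 words the trigger as "If a minimum of one patient shows benefit that is considered significant". The response categories in 9.5.2 include complete and partial response but neither HI nor CRp.

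**The concern.** HI is meant to show that the drug has restored blood production. Erythropoietin, colony stimulating factors and transfusions raise the same three counts, and the scoring rule does not separate the two causes. The trial is open label and non-randomized (4.2), so no comparator carries the same support and reveals the difference.

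Section 9.2.1 estimates clinical and hematological response at each time point, so a single supported count can enter a reported rate. The primary response assessment is after two cycles (4.1), whereas the first scheduled on-treatment marrow is at Cycle 4 (5.2, footnote i). At that assessment the scheduled data for the 6.1 diseases are mainly blood counts, the part most exposed to support.

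The expansion rule tests against a null rate of 0% and needs only one response. Such a rule has no tolerance for responses the drug did not cause, if HI is among the responses it counts.

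**Working it through.** **Which criteria support can satisfy, as written**

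| Criterion | Support that can meet it | What limits this |
|---|---|---|
| HI-E | Red-cell transfusion in a patient not dependent at baseline; erythropoietin in any patient | Dependent patients are scored on transfusion need, which guards against transfusion but not erythropoietin |
| HI-P | Platelet transfusion in a patient not dependent at baseline | For major HI-P, dependent patients are scored on independence |
| HI-N | Therapeutic colony stimulating factor | Major needs both a doubling and a rise above 0.5 x10^9/L |
| CR, CRp | Count component only | Marrow and symptom criteria must still be met |

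Two neutrophil examples, in 10^9/L. From 0.6 to 1.3 the rise is 0.7, or 117%: major. From 0.2 to 0.4 the rise is 0.2, or 100%: minor. For CR, a platelet transfusion that lifts the count past 100 turns a CRp into a CR.

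Transfusion dependence is not defined. The 28-day confirmation in 6.2.1 belongs to CML hematologic response; 6.1 has none.

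**The plan's own figures (9.1.1)**

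- Inputs: null rate 0%, target 15%, power 80%, 10 patients then 30, half-width 0.13.
- Power of at least 1 response in 10 at 15%: 1 − 0.85^10 = 0.803. Reproduced.
- Half-width at n = 30: 1.96 × √(0.15 × 0.85 / 30) = 0.128. Reproduced.
- False-go chance at the 0% null: 1 − 1^10 = 0.

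**What support-only responses would do to the expansion rule**

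Let f be the chance that a patient meets a counted response definition through support alone. The documents give no value, so f is an assumption shown over a range. For an inactive drug the false-go chance in one category is 1 − (1 − f)^10:

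| f | Calculation | False go per category |
|---|---|---|
| 1% | 1 − 0.99^10 | 9.6% |
| 2% | 1 − 0.98^10 | 18.3% |
| 5% | 1 − 0.95^10 | 40.1% |
| 10% | 1 − 0.90^10 | 65.1% |

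**Effect on the estimated rate**

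If the true rate is 15% and f applies to the other 85%, the expected observed rate is 0.15 + 0.85f:

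- f = 5%: 0.15 + 0.0425 = 0.1925, about 19.3%.
- f = 10%: 0.15 + 0.085 = 0.235, or 23.5%.

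The inflation is about 4 to 8.5 points, against a planned half-width of 13 points. Both calculations apply to the expansion rule and the overall response rate only if HI counts as a response.

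**The case against.** The strongest reply is that the plan may never count HI as a response. Section 9.5.2 does not list it, and Section 4.2 asks for significant benefit, which a sensible investigator would not see in a transfusion effect. This stands in part: a reader might take the false-go figures as properties of the trial as designed, and the documents do not support that. Equally, they do not exclude HI. Section 6.1.4 labels its grades as major and minor responses, 9.1.1 does not say which responses count, and significant benefit is undefined. Bias in the HI rates themselves does not depend on this question.

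Two other strong readings fail. A reader might infer that support can produce a CR; it cannot, because the marrow and symptom criteria remain. A reader might also infer that any doubling of the neutrophil count is a major response; the whichever-is-greater wording prevents that.

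There are partial safeguards: the transfusion-dependent branches, the bar on prophylactic colony stimulating factors, and mention of transfusion under relapse after HI (6.1.4.4). None covers a patient first transfused on study, erythropoietin, or therapeutic colony stimulating factor at the moment HI is scored. Section 5.2 refers to consensus criteria, but Section 6 writes out its own definitions, and nothing says that outside criteria override them.

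Finally, efficacy is declared exploratory (9.2.1), and chronic-phase CML falls under 6.2 rather than 6.1. Both narrow the point without removing it.

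**Conclusion.** The concern holds for HI in the diseases covered by Section 6.1. This is more than missing detail: followed literally, the rules give a wrong score, and the error can only push reported HI rates upward. For CR and CRp the effect is limited to the count component in a patient who already meets the other criteria.

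The size of the bias in HI rates cannot be derived from the documents. The consequence for expansion is conditional on two things: that HI counts as a stage 1 response, and the assumed f. Under both, the false-go chance per category runs from 9.6% (f = 1%) to 65.1% (f = 10%) instead of the designed 0%, and a true 15% rate would appear as about 19.3% (f = 5%) or 23.5% (f = 10%). The sample size calculation itself is correct and need not change.

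**What to change.** 1. **Section 6.1.** Require that each count used for CR, CRp or HI be taken outside an interval, fixed in advance by the investigator, after the last support relevant to that count: red-cell transfusion or erythropoietin for hemoglobin, platelet transfusion for platelets, colony stimulating factor for neutrophils. If it is not, that cell line is not scored as HI, and for CR or CRp that count criterion is treated as not met. Tying the rule to the cell line means that a red-cell transfusion does not void a neutrophil or platelet count.
2. **Sections 9.1.1 and 9.5.2.** State whether HI counts as a response for the stage 1 rule, and align the trigger in 4.2 with that statement.
3. **Data collection.** Record the dates of the last transfusion and last growth factor at each response assessment. Concomitant medication is already reviewed at visits, but Section 5.2 mentions transfusion requirement only with the weekly Cycle 1 visits, so this is a small addition.

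These changes affect scoring only; permitted supportive care stays as it is, and enrollment stays at 10 then 30 per category. The cost is a short text change and one or two data fields. The downside is that a few assessments become non-scorable and the reported HI rate may be slightly lower.
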